# Proprietary Information of MD Anderson

Protocol # 2016-0251

Date: February 24, 2020

140

## 12.2 Description of the iRECIST Process for Assessment of Disease Progression

### *Assessment at Screening and Prior to RECIST 1.1 Progression*

Until radiographic disease progression based on RECIST 1.1, there is no distinct iRECIST assessment.

### *Assessment and Decision at RECIST 1.1 Progression*

For subjects who show evidence of radiological PD by RECIST 1.1 as determined by the Investigator, the Investigator will decide whether to continue a subject on study treatment until repeat imaging is obtained (using iRECIST for subject management (see Table 11 and Figure 2). This decision by the Investigator should be based on the subject's overall clinical condition.

Clinical stability is defined as the following:

- Absence of symptoms and signs indicating clinically significant progression of disease
- No decline in ECOG performance status
- No requirements for intensified management, including increased analgesia, radiation, or other palliative care

Any subject deemed clinically unstable should be discontinued from study treatment at site-assessed first radiologic evidence of PD, and is not required to have repeat tumor imaging for confirmation of PD by iRECIST.

If the Investigator decides to continue treatment, the subject may continue to receive study treatment and the tumor assessment should be repeated 4 to 8 weeks later to confirm PD by iRECIST, per Investigator assessment.

Tumor flare may manifest as any factor causing radiographic progression per RECIST 1.1, including:

- Increase in the sum of diameters of target lesion(s) identified at baseline to  $\geq 20\%$  and  $\geq 5$  mm from nadir
  - o Note: the iRECIST publication uses the terminology “sum of measurements”, but “sum of diameters” will be used in this protocol, consistent with the original RECIST 1.1 terminology.
- Unequivocal progression of non-target lesion(s) identified at baseline
- Development of new lesion(s)

iRECIST defines new response categories, including iUPD (unconfirmed progressive disease) and iCPD (confirmed progressive disease). For purposes of iRECIST assessment, the first visit showing progression according to RECIST 1.1 will be assigned a visit (overall) response of iUPD, regardless of which factors caused the progression.

# Proprietary Information of MD Anderson

Protocol # 2016-0251

Date: February 24, 2020

141

At this visit, target and non-target lesions identified at baseline by RECIST 1.1 will be assessed as usual.

New lesions will be classified as measurable or non-measurable, using the same size thresholds and rules as for baseline lesion assessment in RECIST 1.1. From measurable new lesions, up to 5 lesions total (up to 2 per organ), may be selected as New Lesions – Target. The sum of diameters of these lesions will be calculated, and kept distinct from the sum of diameters for target lesions at baseline. All other new lesions will be followed qualitatively as New Lesions – Non-target.

## *Assessment at the Confirmatory Imaging*

On the confirmatory imaging, the subject will be classified as progression confirmed (with an overall response of iCPD), or as showing persistent unconfirmed progression (with an overall response of iUPD), or as showing disease stability or response (iSD/iPR/iCR).

## *Confirmation of Progression*

Progression is considered confirmed, and the overall response will be iCPD, if ANY of the following occurs:

- Any of the factors that were the basis for the initial iUPD show worsening
  - For target lesions, worsening is a further increase in the sum of diameters of  $\geq 5$  mm, compared to any prior iUPD time point
  - For non-target lesions, worsening is any significant growth in lesions overall, compared to a prior iUPD time point; this does not have to meet the “unequivocal” standard of RECIST 1.1
  - For new lesions, worsening is any of these:
    - An increase in the new lesion sum of diameters by  $\geq 5$  mm from a prior iUPD time point
    - Visible growth of new non-target lesions
    - The appearance of additional new lesions
- Any new factor appears that would have triggered PD by RECIST 1.1

## *Persistent iUPD*

Progression is considered not confirmed, and the overall response remains iUPD, if:

- None of the progression-confirming factors identified above occurs AND
- The target lesion sum of diameters (initial target lesions) remains above the initial PD threshold (by RECIST 1.1)

# Proprietary Information of MD Anderson

Protocol # 2016-0251

Date: February 24, 2020

142

Additional imaging for confirmation should be scheduled 4 to 8 weeks from the imaging on which iUPD is seen. This may correspond to the next visit in the original visit schedule. The assessment of the subsequent confirmation imaging proceeds in an identical manner, with possible outcomes of iCPD, iUPD, and iSD/iPR/iCR.

## *Resolution of iUPD*

Progression is considered not confirmed, and the overall response becomes iSD/iPR/iCR, if:

- None of the progression-confirming factors identified above occurs, AND
- The target lesion sum of diameters (initial target lesions) is not above the initial PD threshold.

The response is classified as iSD or iPR (depending on the sum of diameters of the target lesions), or iCR if all lesions resolve.

In this case, the initial iUPD is considered to be pseudo-progression, and the level of suspicion for progression is “reset”. This means that the next visit that shows radiographic progression, whenever it occurs, is again classified as iUPD by iRECIST, and the confirmation process is repeated before a response of iCPD can be assigned.

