# Proprietary Information of MD Anderson

Protocol # 2016-0251

Date: February 24, 2020

34

a subject is clinically stable, additional imaging may be performed to confirm radiographic progression. iRECIST will be used by Investigators to assess tumor response and progression and make treatment decisions as well as for exploratory efficacy analyses where specified.

iRECIST will be used by M.D. Anderson Cancer Center (MDACC) investigators to assess tumor response and progression, and make treatment decisions as well as by M.D. Anderson Department of Diagnostic Imaging in support of all secondary and exploratory response endpoints. Confirmation of PD for iRECIST endpoints will be taken from central imaging (this will be done by Quantitative Imaging Analysis Core [QIAC] at MDACC) retrospectively, according to iRECIST definition.

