# Proprietary Information of MD Anderson

Protocol # 2016-0251

Date: February 24, 2020

143

- o If non-target lesions have never shown unequivocal progression, their doing so for the first time results in iUPD.
- o If non-target lesions have shown previous unequivocal progression, and this progression has not resolved, iUPD results from any significant further growth of non-target lesions, taken as a whole.
- New lesions
  - o New lesions appear for the first time
  - o Additional new lesions appear
  - o Previously identified new target lesions show an increase of  $\geq 5$  mm in the new lesion sum of diameters, from the nadir value of that sum
  - o Previously identified non-target lesions show any significant growth

If any of the events above occur, the overall response for that visit is iUPD, and the iUPD evaluation process (see Assessment at the Confirmatory Imaging above) is repeated. Progression must be confirmed before iCPD can occur.

The decision process is identical to the iUPD confirmation process for the initial PD, with one exception: if new lesions occurred at a prior instance of iUPD, and at the confirmatory imaging the burden of new lesions has increased from its smallest value (for new target lesions, the sum of diameters is  $\geq 5$  mm increased from its nadir), then iUPD cannot resolve to iSD or iPR. It will remain iUPD until either a decrease in the new lesion burden allows resolution to iSD or iPR, or until a confirmatory factor causes iCPD.

Additional details about iRECIST are provided in the iRECIST publication [Seymour et al, 2017].

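### Section 12.2 resets a first iUPD caused only by new or non-target lesions to iSD or iPR while that disease persists, which favours the exploratory iRECIST endpoints

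*Combined protocol and SAP*

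**What the plan says.** All of the following is in Section 12.2 of the combined protocol and SAP unless another place is named.

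- **Entry.** The first scan with RECIST 1.1 progression "will be assigned a visit (overall) response of iUPD, regardless of which factors caused the progression". The listed factors are the target sum (at least 20% and 5 mm above nadir), unequivocal non-target progression, and new lesions.
- **Confirmation (iCPD).** Progression is confirmed if "Any of the factors that were the basis for the initial iUPD show worsening", or if a further RECIST 1.1 progression factor appears. For new lesions, worsening means a rise of 5 mm or more in their sum, visible growth of new non-target lesions, or additional new lesions. For non-target lesions it means significant growth.
- **Persistent iUPD.** Nothing confirms, and "The target lesion sum of diameters (initial target lesions) remains above the initial PD threshold (by RECIST 1.1".
- **Resolution.** Nothing confirms, and "The target lesion sum of diameters (initial target lesions) is not above the initial PD threshold". Then: "The response is classified as iSD or iPR (depending on the sum of diameters of the target lesions), or iCR if all lesions resolve". The episode is labelled pseudo-progression, and the next progression starts again as iUPD.
- **Later episodes.** One exception is added. If new lesions occurred at an earlier iUPD and their burden has risen from its smallest value (by 5 mm or more for new target lesions), the iUPD cannot resolve: "It will remain iUPD until either a decrease in the new lesion burden allows resolution to iSD or iPR".

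On use, Section 4.1 (objective 1) and Section 8.4.1.3 make the iRECIST endpoints exploratory. Sections 3.2 and 8.4.1.2 and Table 17 define the secondary endpoints by RECIST 1.1. Section 4.3.4.4, however, says imaging staff use iRECIST "in support of all secondary and exploratory response endpoints", and Section 4.3.4.2 attaches iRECIST confirmation to ORR, DOR and PFS.

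**The concern.** There are three ways into a first iUPD. Once nothing confirms, only one lesion compartment, the initial target lesions, decides whether it persists or resolves. If those lesions were not the cause, the test says nothing about the disease that was.

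Sections 4.3.4.4 and 7.1.4.1.5 justify waiting for confirmation because some tumours flare and then respond. A new lesion that is still there and has not shrunk is not evidence of that sequence, yet the rule records it as such. The subject may then count as stable or responding under iRECIST, and the progression date moves to a later scan. At stake are the iRECIST response and progression endpoints, and any rate of pseudo-progression reported from them.

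**Working it through.** The plan states no figure for this rule, so the check is logical, with one illustration.

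**Step 1. First iUPD from new or non-target lesions only.** At the iUPD scan the target sum is not above its progression threshold; otherwise it would be one of the causes. At the repeat scan there are three possibilities:

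- The causal disease worsens as defined, or another progression factor appears. Result: iCPD.
- The target sum crosses its threshold for the first time. That is a further RECIST 1.1 factor. Result: iCPD.
- Neither happens. The target sum is below threshold, so the resolution rule applies. Result: iSD or iPR, or iCR if all lesions have gone.

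Persistent iUPD needs a target sum above threshold with nothing confirming. The second possibility rules that out.

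**Step 2. Enumeration.** Every combination at the repeat scan (target sum above or below threshold, target growth of 5 mm or more, non-target worsening, new-lesion worsening) was run through the three rules for each cause. iCR is left out of the table.

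| Cause of first iUPD | Reachable outcomes | New or non-target disease unchanged, targets below threshold |
|---|---|---|
| New lesions | iCPD, iSD/iPR | iSD/iPR |
| Non-target | iCPD, iSD/iPR | iSD/iPR |
| New and non-target | iCPD, iSD/iPR | iSD/iPR |
| Target | iCPD, iSD/iPR, persistent iUPD | iSD/iPR |
| Target and new | iCPD, iSD/iPR, persistent iUPD | iSD/iPR |

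Persistent iUPD is reachable only when target lesions were among the causes.

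**Step 3. Illustration (assumed measurements).** The baseline target sum is 50 mm. At the iUPD scan the targets are 33 mm (33/50 = 0.66, a fall of 34%) and new target lesions sum to 30 mm. At the repeat scan the targets are 33 mm and the new lesions 34 mm.

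- New-lesion change: 34 − 30 = 4 mm, below 5 mm, so not confirming.
- Target threshold from a nadir of 33 mm: 33 × 1.20 = 39.6 mm, which also exceeds 33 + 5 = 38 mm. The sum of 33 mm is below it.
- Result: resolution, graded on a 34% target reduction. Section 12.2 does not restate the partial-response cut-off.
- Measured tumour: 33 + 34 = 67 mm, and 67/50 = 1.34, so 34% above baseline.

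**Step 4. Does the later-episode exception help?** It is written as a departure from the process for the initial progression, so it does not govern the first episode. Its trigger for new target lesions is a rise of 5 mm or more, so even if applied it would not change Step 3.

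**Step 5. Size.** One reclassified subject in an arm of 15 moves a proportion by 1/15 = 6.7 percentage points. For TTP and PFS, suppose scheduled scans only, with the first iUPD at a scheduled scan and confirming growth visible at the next one. If progression is dated at the iUPD scan that opens the confirmed episode, the reset moves it 9 weeks later, or 9 + 9 = 18 weeks if the next scheduled scan is skipped because it falls less than 4 weeks after the repeat scan. If it is dated at the confirming scan, the shift is the extra 4 to 8 weeks needed to confirm again. These are illustrations, because Section 7.1.4.1.2 allows earlier imaging.

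**The case against.** The strongest replies, and what stands of each:

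- **Resolution is not decided by target lesions alone.** This is right. Significant non-target growth, visible growth of new non-target lesions, additional new lesions, or a rise of 5 mm or more in the new-lesion sum each block it. What the rule never asks is that the causal disease shrink or disappear.
- **The effect is mainly exploratory.** This stands. The secondary endpoints and the key ORR in Table 15 are per RECIST 1.1. No decision rule names an iRECIST response, so the signal of at least one response in Section 8.6.1 would be touched only if iRECIST responses were counted toward it.
- **A single iPR is not a confirmed response, and DCR requires stable disease for 24 weeks before any sign of progression.** Section 7.1.4.1.2 does ask for confirmation at 4 weeks or later, and the DCR wording may exclude some of these subjects. Confirmation does not remove the problem, because unchanged new lesions trigger no fresh iUPD at later visits.
- **Section 12.2 points to the iRECIST publication for details.** That source was not consulted, and no departure from it is claimed. The point concerns the rule as the protocol states it.

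A reader might go further and infer that Section 12.2 contradicts itself, with the same unchanged new lesions giving iSD in a first episode and iUPD in a later one. The text does not support that. The exception applies only when new-lesion burden has risen from its smallest value, so new lesions that have stayed the same since they appeared resolve in both. Nor is it inconsistent that iCR requires all lesions to resolve while iPR does not.

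**Conclusion.** The point holds in a limited form. A first iUPD caused only by new or non-target lesions cannot persist under Section 12.2. Without confirmation it is reset to iSD or iPR although the cause may be unchanged, or, for new target lesions, up by less than 5 mm. This follows from the text and rests on no assumption about growth rates.

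For an affected subject the category can only stay the same or become more favourable, and progression can only move later. That biases the exploratory iRECIST ORR, DCR, TTP and PFS favourably, and DOR for a responder whose later new lesions are reset. OS does not depend on the classification. The RECIST 1.1 secondary endpoints are affected only so far as Sections 4.3.4.2 and 4.3.4.4 bring iRECIST into them.

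A reader might also want a percentage of growing lesions that escape confirmation, or a fixed minimum delay. The documents support neither: they give no lesion growth rates or reading error, and imaging may be done early. The number of affected subjects among about 15 per arm is unknown. The change is worth making because the bias comes from a stated rule and is cheap to remove.

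**What to change.** For the iRECIST endpoints derived from the retrospective central read by the imaging core (Section 4.3.4.4), tie both rules to the factor or factors that caused the iUPD:

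- **Stays iUPD:** nothing confirms, and at least one causal factor is still present without regression (target sum above threshold, new-lesion burden not decreased, or non-target progression not regressed).
- **Resolves:** nothing confirms, and every causal factor has regressed.

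This is a new criterion and should be labelled as one; it is not the existing later-episode exception. Before the reads, state what counts as a decrease in new-lesion burden and as non-target regression, and which date a confirmed progression carries. State also that the next available scan serves for confirmation. Subjects whose iUPD resolved on site return to the 9-week schedule: after a repeat scan at 8 weeks, the next scheduled scans fall 9 − 8 = 1 and 18 − 8 = 10 weeks later, both outside the 4 to 8 week window. Report the classification as written as a sensitivity analysis.

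The cost is some derivation work and slightly less favourable exploratory figures. No scans are added if the change is confined to the retrospective derivation. Section 7.1.4.1.5, Table 11, and the repeat-imaging and management text in Section 12.2 use the same classification. The sponsor must reconcile them with it; no clinical rule is proposed here.

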## *Management Following the Confirmatory Imaging*

If repeat imaging does not confirm PD per iRECIST, as assessed by the Investigator, and the subject continues to be clinically stable, study treatment may continue and follow the regular imaging schedule. If PD is confirmed, subjects will be discontinued from study treatment.

NOTE: If a subject has confirmed radiographic progression (iCPD) as defined above, but the subject is achieving a clinically meaningful benefit, an exception to continue study treatment may be considered following consultation with Merck. In this case, if study treatment is continued, tumor imaging should continue to be performed following the intervals as outlined in Section 6.

## *Detection of Progression at Visits After Pseudo-progression Resolves*

After resolution of pseudo-progression (ie, achievement of iSD/iPR/iCR), iUPD is indicated by any of the following events:

- Target lesions
  - Sum of diameters reaches the PD threshold ( $\geq 20\%$  and  $\geq 5$  mm increase from nadir) either for the first time, or after resolution of previous pseudo-progression. The nadir is always the smallest sum of diameters seen during the entire trial, either before or after an instance of pseudo-progression.
- Non-target lesions

# Proprietary Information of MD Anderson

Protocol # 2016-0251

Date: February 24, 2020

143

- o If non-target lesions have never shown unequivocal progression, their doing so for the first time results in iUPD.
- o If non-target lesions have shown previous unequivocal progression, and this progression has not resolved, iUPD results from any significant further growth of non-target lesions, taken as a whole.
- New lesions
  - o New lesions appear for the first time
  - o Additional new lesions appear
  - o Previously identified new target lesions show an increase of  $\geq 5$  mm in the new lesion sum of diameters, from the nadir value of that sum
  - o Previously identified non-target lesions show any significant growth

If any of the events above occur, the overall response for that visit is iUPD, and the iUPD evaluation process (see Assessment at the Confirmatory Imaging above) is repeated. Progression must be confirmed before iCPD can occur.

The decision process is identical to the iUPD confirmation process for the initial PD, with one exception: if new lesions occurred at a prior instance of iUPD, and at the confirmatory imaging the burden of new lesions has increased from its smallest value (for new target lesions, the sum of diameters is  $\geq 5$  mm increased from its nadir), then iUPD cannot resolve to iSD or iPR. It will remain iUPD until either a decrease in the new lesion burden allows resolution to iSD or iPR, or until a confirmatory factor causes iCPD.

Additional details about iRECIST are provided in the iRECIST publication [Seymour et al, 2017].

# Proprietary Information of MD Anderson

Protocol # 2016-0251

Date: February 24, 2020

144

## 12.3 HBV Definitions and Treatment Considerations

Table 20 describes the various definitions of hepatitis B as well as the treatment considerations for subjects with HBV:

Protocol will exclude history of HBV infection with viral load detectable by qPCR testing (with sensitivity to detect at least a minimum of 20 IU/mL); unless initiation of treatment with nucleotide analogs such as those used in the treatment of HBV (eg, lamivudine, adefovir, tenofovir, telbivudine, entecavir), is entertained and hepatitis B virus becomes undetectable.

Table 20 Hepatitis B Definitions and Treatment Considerations

Test	Patient Status	Any HBV Treatment Needed?
HBsAg (-) Total anti-HBc (+) HBsAb (+)	Immune after natural infection	No
HBsAg (-) Total anti-HBc (-) HBsAb (+)	Immune after vaccination	No
HBsAg (+) Total anti-HBc (+) IgM anti-HBc (+) HBsAb (-)	Acute infection	—
HBsAg (+) Total anti-HBc (+) IgM anti-HBc (-) HBsAb (-)	Chronic infection	Yes, need to be on a HBV treatment for at least 12 weeks prior to start of pembrolizumab without evidence of a flare during that period Exclude if: (a) <12 weeks of therapy; (b) HBV DNA not under control during this time frame; (c) Documented HBV flare in the past 12 weeks
HBsAg (-) Total anti-HBc (+) IgM anti-HBc (-) HBsAb (-) HBV DNA (negative)	Unclear. Could be: (1) Resolved infection (2) False positive anti-HBc (3) Low level infection (4) Resolving Acute infection	No
HBsAg (-) Total anti-HBc (+) IgM anti-HBc (-) HBsAb (-) HBV DNA (+)	(5) Low level infection (6) Resolving acute infection	Yes (as above)

# Proprietary Information of MD Anderson

Protocol # 2016-0251

Date: February 24, 2020

145

## 12.4 Common Terminology Criteria for Adverse Events

The descriptions and grading scales found in the revised NCI Common Terminology Criteria for Adverse Events (CTCAE) version 4.0 will be utilized for adverse event reporting. (<http://ctep.cancer.gov/reporting/ctc.html>).

## 12.5 Child-Pugh Score

The Child-Pugh score is used to assess the prognosis of chronic liver disease, mainly cirrhosis. Although it was originally used to predict mortality during surgery, it is now used to determine the prognosis, as well as the required strength of treatment and the necessity of liver transplantation.

### Scoring

The score employs five clinical measures of liver disease. Each measure is scored from 1 to 3, with 3 indicating most severe derangement (Table 21).

Table 21      Child-Pugh Scoring

Measure	1 point	2 points	3 points
Total bilirubin (μmol/L or mg/dL)	<34 or <2	34–51 or 2–3	>51 or >3
Serum albumin (g/dL)	>3.5	2.8–3.5	<2.8
Prothrombin time, prolongation (sec)	<4.0	4.0–6.0	>6.0
Ascites	None	Mild	Moderate to Severe
Hepatic encephalopathy	None	Grade 1-2 (or suppressed with medication)	Grade 3–4 (or refractory)

In primary sclerosing cholangitis and primary biliary cirrhosis, the bilirubin references are changed to reflect the fact that these diseases feature high conjugated bilirubin levels. The upper limit for 1 point is 68 μmol/L (4 mg/dL) and the upper limit for 2 points is 170 μmol/L (10 mg/dL).

